### **Costs to the Subject**

• Describe and justify any costs that the subject will incur as a result of participation; ordinarily, subjects should not be expected to pay for research without receiving direct benefit.

If the participant does not have an unlimited data plan, additional phone costs may incur. All other study costs, including any procedures related directly to the study, will be paid for by the study.

# **Data Analysis & Statistical Considerations**

Describe endpoints and power calculations. Provide a detailed description of how study data will be
analyzed, including statistical methods used, and how ineligible subjects will be handled and which
subjects will be included for analysis. Include planned sample size justification. Provide estimated time
to target accrual and accrual rate. Describe interim analysis including plans to stop accrual during
monitoring. Phase I studies, include dose escalation schema and criteria for dose escalation with
definition of MTD and DLT.

Hypothesis testing will be conducted using generalized mixed models, which are well-equipped to handle missing data, even when data is missing not completely at random. Multiple imputation will also be used to further address potential bias resulting from missing data.

Specific Aim 1 will examine the effects of NNCs versus VLNCs on: a) changes in cigarettes smoked per day, nicotine dependence, withdrawal symptoms and pain across the 5 weekly visits (V1 through V5), and b) pre-post intervention changes in withdrawal and pain following 24hr abstinence. For both sets of models, Group will be entered as a between-subjects factor with 2 levels (NNC or VLNC), and Session will be included as a within-subjects factor with 5 (week) or 2 (pre- vs post-intervention) levels. Baseline pain and FTCD scores, assessed at screening, will be included along with sex as covariates. We predict that the VLNC group will exhibit decreasing nicotine dependence and smoking frequency across the 4 weeks of study cigarette use, with no change for the NNC group (i.e., Group x Week interactions). Based on our prior work, we predict only a minimal increase in withdrawal during the first week of VLNC use, with no group differences in withdrawal or pain during remaining weekly visits. During 24-hr abstinence, we predict a Group x Session interaction, such that the VLNC group will exhibit pre- to post-intervention decre ases in withdrawal and pain, with no change for the NNC group. Secondary analyses will evaluate effects of abstinence, controlling for weekly changes during ad lib smoking, by including withdrawal and pain assessed at V1 (pre-intervention) and V5 (post-intervention) as time-varying covariates.

Specific Aim 2 will be to examine the effects of NNCs versus VLNCs on the bidirectional, within-person associations between momentary reports (assessed with EMA) of pain, negative affect, and smoking urge and behavior. Longitudinal associations between smoking/smoking urge and a) pain intensity, b) pain interference, and c) negative affect will be evaluated in separate models. The first set of models will examine each pain measure as a predictor of smoking urge/intent to smoke at each time point. The second set of models will examine recent smoking (i.e., having smoked within the past 15 minutes) as a predictor of each pain measure. Models will include repeated assessments (Level 1) nested within participants (Level 2), nested within weeks (Level 3), with random intercepts. Cigarette condition (NNC or VLNC) and its interaction with week will then be entered to examine the moderating effects of study cigarette use on these within-person associations.

Exploratory Aim 3 will examine the effects of NNCs versus VLNCs on pre- to-post-intervention changes in smoking for pain-related cognitions, assessed at V1 and V5, including smoking to cope with pain, interest in quitting smoking, quit self-efficacy, pain catastrophizing, and pain self-efficacy. For each model, Group will be entered as a between-subjects factor, and Session will be entered as a within-subjects factor.

Sensitivity Analyses will examine the potential impact of a) VLNC compliance (described above) and b) non-opioid analgesic use on the results of primary analyses. Analgesic use will be coded as yes/no at screening and at each weekly visit for the following medication classes: NSAIDS, anticonvulsants, antidepressants, other CNS depressants, muscle relaxants, migraine medications, and corticosteroids. Sensitivity analyses will then examine the impact of weekly use of each medication class as time-varying covariates in primary models.

Sample size determination. Sample size was estimated using G\*Power 3.1, assuming 85% power at alpha=0.05 for detecting group by session interactions in Aim 1 (see Statistical Design and Power for additional details). For effect sizes corresponding to Cohen's d = 0.4 to 0.6, assuming a conservative estimate of the correlation between repeated measurements of 0.4, our proposed sample size of 48 will provide 90% to 99% power for detecting group by weekly session interactions (5 measurement occasions per group), and 70% to 96% power for detecting group by abstinence session interactions (2 measurement occasions per group). Importantly, power for detecting abstinence session interactions is improved (ranging from 77% to 98%) if repeated measures correlation is higher, as suggested by our preliminary data. These calculations also do not take into account the inclusion of baseline covariates that are likely to improve power.  Moreover, a loss of 33% of the sample due to VLNC non-compliance during sensitivity analyses will still yield statistical power of 96% and 78% for analyses with 5 measurement occasions or 2 measurement occasions, respectively, under a moderate scenario in which Cohen's d = 0.5and the correlation between repeated measures = 0.5. Given the increase in statistical power associated with EMA due to a) decreasing error variance,  and b) increasing the number of repeated assessments,  it is expected that sample sizes estimates determined for Aims 1 and 3 will provide ample power for detecting group differences in reciprocal smoking-pain associations in Aim 2.

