### **Standard Research Summary**

### **Purpose of the Study**

Objectives & hypotheses to be tested

The purpose of the study is to evaluate the effects of switching to VLNC cigarettes as a potential strategy for disrupting the pain-smoking reinforcement and withdrawal cycle among smokers with chronic back pain. Adult daily smokers with chronic (> 3 months) non-cancer back pain will be randomly assigned to 4-weeks of Normal Nicotine Content (NNC) or VLNC investigational cigarette use. Participants will attend weekly assessment visits during this time, and will complete EMA assessments during a baseline week of usual brand smoking, and during weeks 1 and 4 of study cigarette use. Participants will also complete assessments of pain and withdrawal following 24 hours abstinence at the start of the study and after 4 weeks of study cigarette use.

Aim 1 will examine effects of NNCs versus VLNCs on smoking and pain over the 4 weeks of study cigarette use and during the 24-hour abstinence tests.

Hypothesis 1a: VLNCs will lead to reductions in nicotine dependence and frequency of smoking over the course of study cigarette use, whereas no change will be observed for NNCs.

*Hypothesis 1b:* Relative to the pre-intervention baseline, smokers assigned to VLNCs will report decreased pain intensity and interference and fewer withdrawal symptoms during the post-treatment 24-hr abstinence test compared with smokers in the NNC condition.

Aim 2 will examine effects of NNCs versus VLNCs on the bidirectional, within-person associations between momentary reports (as assessed with EMA) of smoking urge/behavior, pain and negative affect.

Hypothesis 2a: VLNCs will reduce the magnitude of the within-person associations between momentary reports of pain/negative affect and smoking urge/intent to smoke.

Hypothesis 2b: VLNCs will reduce the magnitude of the within-person association between recent smoking and reports of decreased pain and negative affect.

**Exploratory Aim 3** will examine the effects of NNCs versus VLNCs on changes in smoking and pain-related cognitions, including interest in quitting smoking, abstinence self-efficacy, and smoking to cope with pain.

*Hypothesis:* Following VLNCs, participants will report increased motivation and intention to quit smoking, greater abstinence self-efficacy, and decreased use of smoking as a pain-related coping strategy.

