Baseline Abstinence/Training Session. Following screening, participants will complete a baseline abstinence challenge session, in which they are asked to abstain from smoking for 24 hours prior to the session. Expired CO < 6 ppm or 50% reduction from baseline will be used to verify abstinence. Participants will complete measures of craving, pain, and withdrawal. At the conclusion of the session, Metric Wire software will be installed on their smartphone, and they will be trained in the procedures for EMA.

Weekly Sessions. After one week of baseline EMA while smoking of usual brand cigarettes, participants attend an in-person visit (V1), during which they will be randomized to NNC or VLNC condition, given a supply of study cigarettes, and provided with a schedule of 4 weekly follow-up visits (V2 through V5). During each of the weekly visits participants will complete self-report measures and a timeline follow-back of past-week smoking, other tobacco use and alcohol/substance use; additional study cigarettes will be supplied; and breath CO and urinary measures of nicotine exposure will be collected. Adverse events will be monitored, as well as changes in medical history including new or discontinued medications, new treatments for current medical problems, or other study participation.

Post-Intervention Abstinence Session. Immediately following the final weekly visit, participants will be asked to abstain from smoking for 24 hours prior to attending a final laboratory abstinence session. Procedures and measures will be identical to those used in the initial abstinence session.

Follow-Up 3-Month Phone Call. Participants will be contacted by phone 3 months after completing the study to provide information about current smoking, recent quit attempts, and cessation strategies used.

Table 1. Schedule of Events and Procedures

CIGARETTES		UB	NNC	NNC or VLNC Cigarettes							
REMOTE ASSESSMENT		EMA			E			EMA			
IN-PERSON VISITS	Screening	24hr / Test 1 Traini (A1)	./ ng	Visit Week 1 (V1)	Visit Week 2 (V2)	Visit Week 3 (V3)	Visit Week 4 (V4)	Visi We 5 (V5	ek A	ABS Test 2 A2)	
Study Day	-30 to -1	0		7	14	21	28	35	3	36	
Window (in days)		0		(± 2)	(± 2)	(± 2)	(± 2)	) (±	2) (	± 1)	
PROCEDURES					-						
Informed Consent	Х								Î		
Eligibility	Х										
Demographics	Х										
Medical History	Х										
Tobacco History	Х										
Breath CO Sample	Х	Х		X	Х	Х	Х	Х	>	(	
Breath Alcohol	Х	Х		X	Х	Х	Х	Х	>	(	
Urine Drug Screen	х										

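### Hypothesis 1b: the pre-randomisation abstinence score is an outcome level, not a covariate; the planned test is valid but less precise than one that conditions on that score

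*Combined protocol and SAP*

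**What the plan says.** Hypothesis 1b, under Purpose of the Study, predicts: "Relative to the pre-intervention baseline, smokers assigned to VLNCs will report decreased pain intensity and interference and fewer withdrawal symptoms" at the post-treatment 24-hour abstinence test, compared with the NNC arm.

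The timing is in Design & Procedures. For A1: "Following screening, participants will complete a baseline abstinence challenge session". One week of usual-brand smoking follows, and then "participants attend an in-person visit (V1), during which they will be randomized to NNC or VLNC condition". Table 1 puts A1 at study day 0 and V1 at day 7, so A1 is a pre-randomisation measurement of the Hypothesis 1b outcomes.

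The model is in Data Analysis & Statistical Considerations, Specific Aim 1: "Session will be included as a within-subjects factor with 5 (week) or 2 (pre- vs post-intervention) levels". The test is named there too: "During 24-hr abstinence, we predict a Group x Session interaction". On covariates: "Baseline pain and FTCD scores, assessed at screening, will be included along with sex as covariates". A1 pain and A1 withdrawal are not listed, and no covariate-by-Session term is mentioned. A secondary analysis adds the V1 and V5 values as time-varying covariates; that does not condition on A1.

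The sample size paragraph describes the calculation as "assuming 85% power at alpha=0.05 for detecting group by session interactions in Aim 1". For 48 participants and two occasions it reports 70% to 96% power: "For effect sizes corresponding to Cohen's d = 0.4 to 0.6, assuming a conservative estimate of the correlation between repeated measurements of 0.4". It gives 77% to 98% if the correlation is higher, and adds that baseline covariates, left out of the calculation, should raise power.

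**The concern.** A baseline value taken before randomisation has the same expected mean in both arms. A model that uses this, by conditioning on A1 or by holding the arm means equal at A1, estimates the same between-arm effect as a comparison of change scores. It does so with a variance that is no larger, apart from a small-sample penalty. The planned two-level Group x Session model leaves the A1 means free in each arm and so gives up that precision.

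The plan's own low-end power for this test, 70% at d = 0.4, is below the 85% it names. A1 is already collected, so the lost precision could be recovered without new data. The sample size paragraph also looks to baseline covariates for extra power, but the listed ones, entered additively, cannot supply it for this contrast.

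**Working it through.** **Inputs.** N = 48 (24 per arm), two-sided alpha 0.05, d = 0.4 to 0.6, correlation rho = 0.4 or 0.5: all from the documents. The A2/A1 SD ratio k is not given; I use 0.8, 1 and 1.25 as assumptions. rho = 0.7 is also an assumption.

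**1. Reproduce the plan's power.** Repeated-measures interaction with f = d/2, noncentrality lambda = f² x N x m/(1 - rho), and (m - 1) and (N - 2)(m - 1) degrees of freedom. For m = 2, d = 0.4 and rho = 0.4, lambda = 0.04 x 48 x 2/0.6 = 6.4.

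| rho | d = 0.4 | d = 0.5 | d = 0.6 |
|---|---|---|---|
| 0.4 | 69.7% | 87.2% | 96.0% |
| 0.5 | 77.4% | 92.4% | 98.3% |

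These match the stated 70% to 96% and 77% to 98%. On this scale d = 0.4 is a between-arm difference in change of 0.8 SD.

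**2. Variance of the two contrasts.** With the A1 SD set to 1 and the A2 SD to k:
- change score: 1 + k² - 2·rho·k
- conditional on A1: k²(1 - rho²)

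| k | rho | Change | Conditional | Cut |
|---|---|---|---|---|
| 1 | 0.4 | 1.20 | 0.84 | 30% |
| 1 | 0.5 | 1.00 | 0.75 | 25% |
| 1.25 | 0.4 | 1.5625 | 1.3125 | 16% |
| 1.25 | 0.5 | 1.3125 | 1.1719 | 11% |
| 0.8 | 0.4 | 1.00 | 0.5376 | 46% |
| 0.8 | 0.5 | 0.84 | 0.48 | 43% |
| 1.25 | 0.7 | 0.8125 | 0.7969 | 2% |

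Estimating one slope with 48 participants multiplies the conditional variance by about 1 + 1/44. The first four cuts become about 28%, 23%, 14% and 9%, and the last becomes nil.

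**3. Power after conditioning on A1.** Equal SDs, penalty included: divide lambda by ((1 + rho)/2)(1 + 1/44) and use 45 error degrees of freedom.

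| rho | d = 0.4 | d = 0.5 | d = 0.6 |
|---|---|---|---|
| 0.4 | 83.3% | 95.5% | 99.2% |
| 0.5 | 87.2% | 97.2% | 99.6% |

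The smallest d with 85% power falls from 0.48 to 0.41 (rho 0.4) and from 0.44 to 0.39 (rho 0.5). Simulation of 40,000 trials at d = 0.4 agrees: 69.5% against 83.3%, and 77.3% against 87.3%, with type I error of 4.9% to 5.2%. At k = 1.25, with planned power held at 70% and 77%, the adjusted figures are 76% and 81%.

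**4. Screening covariates in the current model.** A covariate that adds the same amount at both sessions drops out of each participant's change. In a mixed model fitted to simulated complete data, the Group x Session estimate was -0.1513 (SE 0.2737) with and without a screening score and sex. With 20% of A2 missing at random, the ratio of standard errors was 0.993.

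**5. Covariance structure when A1 stays in the response.** I simulated the model with equal A1 means and a random-intercept covariance under the null (24 per arm, 4,000 trials per setting). Type I error was about 7% to 9% at k = 1.25 and 9% to 10% at k = 1.5. It was near 5% at k = 1 and about 2% to 3% at k = 0.8. In similar runs the planned change contrast and the model of A2 on A1 stayed between 4.6% and 6.2%.

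**The case against.** The strongest defence is that the plan matches its hypothesis. Hypothesis 1b predicts a fall in one arm and no change in the other, and Group x Session tests exactly that. A reader might infer from this point that the planned test is biased or invalid. The documents do not support that: A1 precedes randomisation and the change contrast keeps its type I error.

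A reader might also infer that Hypothesis 1b is underpowered. On the plan's own scale that holds only at the low end. At d = 0.5 planned power is 87% or 92%. At d = 0.4 it reaches 85% once rho is about 0.59, and the plan says its preliminary data suggest a correlation above 0.4. Conditioning on A1 at d = 0.4 and rho = 0.4 still gives 83%, just short of the target.

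The size of the gain depends on an SD ratio the documents do not state, and in the unfavourable corner it vanishes. That stands, and it is why a range is given. It does not remove the case for the change, which costs little and gains something over most of the range.

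Nor does the point carry over to the weekly outcomes. The gain there depends on the shape of the effect and the covariance, and stated power is already 90% to 99%. How d is defined is a separate reporting question. If d were itself the difference in change, planned power at rho 0.4 would be 24% to 46%, and conditioning on A1 would raise it only to 31% to 59%.

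**Conclusion.** The point holds as one of efficiency, confined to the A1/A2 comparison in Hypothesis 1b. The planned test is valid but does not use the pre-randomisation A1 value as well as it could. The large-sample variance saving is 25% to 30% with equal SDs at the plan's correlations, 11% to 16% if the A2 SD is a quarter larger, 43% to 46% if it is a fifth smaller, and close to nil at SD ratio 1.25 with correlation 0.7. With equal SDs, power at d = 0.4 gains 13 to 14 points at rho 0.4 and about 10 at rho 0.5.

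The equivalence with a change score assumes complete data and an identity link. The remark on baseline covariates and power is not borne out for the current contrast if those covariates enter additively. It may become true once A1 is conditioned on: in simulation at d = 0.4, two screening covariates correlated 0.3 with both sessions brought power to 84% (rho 0.4), against 80% when all three were uninformative.

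**What to change.** For Hypothesis 1b, pre-specify a model of A2 on group with A1 of the same outcome as a covariate, keeping screening pain, screening FTCD and sex. Within-arm changes can still be reported descriptively.

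An alternative keeps A1 and A2 in the response with the arm means constrained equal at A1. Use it only with an unstructured covariance (separate A1 and A2 variances) and small-sample degrees of freedom, because a random-intercept covariance inflates type I error when the A2 SD is the larger.

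In the sample size paragraph, limit the covariate remark: in the current model, screening covariates entered additively do not improve the Group x Session contrast (exactly so with complete data and an identity link), although they may help once A1 is conditioned on.

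The cost is wording and a few degrees of freedom; no new data are needed. A1 uses about one. If the three screening covariates carry nothing beyond A1, power at d = 0.4 with equal SDs is about 80% (rho 0.4) and 85% (rho 0.5) instead of 83% and 87%. In the unfavourable corner (SD ratio 1.25, rho 0.7) the same four covariates would lose some precision: 0.7969 x (1 + 4/41)/0.8125 = 1.08, a variance about 8% larger than that of the change score.

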Tobacco smoking and chronic pain are highly comorbid conditions. Nicotine has been shown to provide mild, short-term anti-nociceptive effects, which may contribute to powerful negative reinforcement learning. Conversely, smoking withdrawal exacerbates pain, presenting a potential barrier to smoking cessation. The goal of the proposed research is to examine whether switching to Very Low Nicotine Content (VLNC) cigarettes can directly weaken the pain-smoking reinforcement cycle, and attenuate withdrawal-induced hyperalgesia, among smokers with chronic pain, in order to better understand the mechanisms underlying smoking-pain comorbidity. Adult, non-treatment seeking daily smokers with chronic (> 3 months) non-cancer back pain will complete 1-week of baseline ecological momentary assessment (EMA) while smoking their usual brand of cigarettes to familiarize them with study procedures; they will then be randomized to 4-weeks of Normal Nicotine Content (NNC) or VLNC cigarettes. EMA will continue during weeks 1 and 4 of study cigarette use, and will assess smoking behavior and urge, negative affect, and pain intensity and interference. Participants will attend weekly in-person visits to obtain biomarker verification of cigarette compliance, and will complete measures of nicotine dependence, selfefficacy and motivation to quit, and pain-related coping. At the start of the study and at the end of 4weeks of study cigarette use, a 24-hr smoking abstinence test will be used to assess withdrawal symptoms and withdrawal-induced hyperalgesia. Participants will also be contacted by telephone 3 months after study participation to assess quitting behaviors, including actual quit attempts and use of cessation strategies. Analyses will examine the effects of NNCs versus VLNCs on pain and smoking-related measures assessed during EMA, weekly visits, and pre- and post-intervention abstinence tests. Risks of the study include withdrawal symptoms during the 24-hr abstinence sessions and during initial use of VLNCs, risks associated with smoking investigational cigarettes, and risks associated with the collection of personal information.

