### **Risk/Benefit Assessment**

• Include a thorough description of how risks and discomforts will be minimized (per 45 CFR 46.111(a) (1 and 2)). Consider physical, psychological, legal, economic and social risks as applicable. If vulnerable populations are to be included (such as children, pregnant individuals, imprisoned persons or cognitively impaired adults), what special precautions will be used to minimize risks to these subjects? Also identify what available alternatives the person has if he/she chooses not to participate in the study. Describe the possible benefits to the subject. What is the importance of the knowledge expected to result from the research?

Potential Risks: Continuing to smoke carries significant health risks. Participants enrolling in this study are not attempting to quit smoking, and will not be provided with smoking cessation treatment. However, participants will be provided with referral information for smoking cessation at the conclusion of the study. Use of VLNCs provided during the study does not pose any reduced risk relative to typical combustible cigarettes. There is a risk that participants in the VLNC condition could increase their smoking to compensate for lack of nicotine. Although infrequent, use of study cigarettes may also contribute to other adverse effects, including throat irritation, coughing, or nausea. There is also the risk that smokers assigned to the VLNC condition will experience increased withdrawal symptoms, including increased pain or negative affect due to decreased nicotine intake. All participants will be advised of potential symptoms and provided with coping strategies and support as necessary. Subjects may also experience withdrawal symptoms during 24-hr abstinence period. Finally, there is a risk attendant to the confidentiality of psychological data and self-report data.

There are no direct benefits to participants, but the study will increase knowledge of the role of nicotine and non-nicotine factors in the comorbidity between smoking and pain, and the effects of VLNCs on clinically-relevant outcomes among smokers with chronic pain. This information will aid in the development and evaluation of new and more effective treatments for smokers with pain. Given minimal risks of participation, we consider the risk/benefit ratio acceptable and representing an appropriate level of risk for human participation. Steps taken to minimize risks to participants are described below.

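### The secondary abstinence analysis adjusts for V5 pain and withdrawal, which are post-randomisation outcomes; if VLNCs shift V5, it does not estimate the abstinence increment

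*Combined protocol and SAP*

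**What the plan says.** All references are to the combined protocol and SAP.

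- **Purpose of the abstinence sessions.** The Research Abstract says that "a 24-hr smoking abstinence test will be used to assess withdrawal symptoms and withdrawal-induced hyperalgesia". Hypothesis 1b (Purpose of the Study) concerns levels in that test: "decreased pain intensity and interference and fewer withdrawal symptoms during the post-treatment 24-hr abstinence test".
- **Primary analysis.** Under Data Analysis & Statistical Considerations, Specific Aim 1, this is Group x Session on the two abstinence sessions, A1 and A2.
- **Secondary analysis.** The same paragraph then isolates abstinence from change during ad lib smoking "by including withdrawal and pain assessed at V1 (pre-intervention) and V5 (post-intervention) as time-varying covariates".
- **V5 as an outcome.** The first part of Aim 1 analyses "changes in cigarettes smoked per day, nicotine dependence, withdrawal symptoms and pain across the 5 weekly visits (V1 through V5".
- **Timing.** Under Design & Procedures, "participants attend an in-person visit (V1), during which they will be randomized to NNC or VLNC condition". The second abstinence session comes at the end: "Immediately following the final weekly visit, participants will be asked to abstain from smoking for 24 hours". Table 1 puts A1, V1, V5 and A2 on days 0, 7, 35 and 36.
- **Expected V5 difference.** Specific Aim 1 predicts a minimal rise in withdrawal in week 1, "with no group differences in withdrawal or pain during remaining weekly visits". The Risk/Benefit Assessment lists as a VLNC risk "increased withdrawal symptoms, including increased pain or negative affect due to decreased nicotine intake".

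The plan gives no contrast of A2 - V5 with A1 - V1, and does not say how to read the adjusted result if V5 differs by arm.

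**The concern.** The secondary model is the only single model in the plan that tries to separate withdrawal-induced pain from a general change in pain on study cigarettes. It does so by conditioning on a variable that assignment may have changed.

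Regression adjustment removes only the fitted slope times the V5 difference, whereas the abstinence increment requires removing the whole difference. If V5 differs by arm, part of an ad lib change is left in the term that will be read as the abstinence effect.

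The interpretation is also at stake. If reduced nicotine raises everyday pain at V5 and abstinent pain at A2 is unchanged, the step from V5 to A2 shrinks. Any analysis that separates the two can then show a smaller abstinence effect although nobody has less pain when abstinent. The plan has no rule for recognising this.

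**Working it through.** **Inputs from the documents.** 24 per arm (Overview of Study Design). Repeated-measures correlation 0.4, and 0.5 in the moderate scenario; d = 0.4 to 0.6; alpha 0.05 (Sample size determination).

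**Assumptions.** SD 1 at every visit; same-phase correlation r between ad lib and abstinent scores of 0.6 to 0.8; V5 shift 0.5 SD; pain-withdrawal correlation 0.4; random-intercept model. The documents give none of these for Aim 1.

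1. **The plan's own power figure.** Take f = d/2 and lambda = f² x N x m/(1 - rho), with N = 48, m = 2 and rho = 0.4. Then d = 0.4 gives 0.04 x 48 x 2/0.6 = 6.4 and power 69.7%; d = 0.6 gives 14.4 and 96.0%. The stated 70% and 96% reproduce. They cover the primary interaction, not the secondary model.

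2. **What each analysis estimates for pain.** Let b be the fitted pain slope and c the fitted withdrawal slope.
   - Planned term = (A2 shift) - b x (V5 pain shift) - c x (V5 withdrawal shift).
   - Increment = (A2 shift) - (V5 pain shift).
   - Miss = (1 - b) x (V5 pain shift) - c x (V5 withdrawal shift).

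   With no V5 shift the miss is zero.

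3. **Size in large samples.** With the pain covariate only and cross-phase correlation 0.4, b is 0.58 at r = 0.6 and 0.80 at r = 0.8. The miss is (1 - 0.58) x 0.5 = 0.21 and (1 - 0.80) x 0.5 = 0.10 SD. With withdrawal, screening pain, FTCD and sex added (cross-phase 0.4 to 0.5), b is 0.43 to 0.50 at r = 0.6 and 0.72 to 0.75 at r = 0.8. The miss is then 0.25 to 0.29 and 0.11 to 0.14 SD.

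   In a variant with c of 0.11 to 0.15 and r of 0.6 to 0.8, a pain shift alone leaves 0.15 to 0.30 SD. Equal pain and withdrawal shifts leave 0.09 to 0.24.

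4. **At 24 per arm** (all covariates, r 0.6 to 0.8, cross-phase 0.4 to 0.5): mean estimate, and rejection at nominal 5%.

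| Case | Planned V5-adjusted model | A2 - V5 adjusted for A1 and V1 |
|---|---|---|
| V5 up 0.5, A2 unchanged (increment -0.5) | -0.22 to -0.38; 11-34% | -0.49 to -0.50; 41-72% |
| V5 and A2 both down 0.5 (increment 0) | -0.12 to -0.27; 8-15% | 0.00 to 0.01; 3-5% |
| V5 unchanged, A2 down 0.5 (increment -0.5) | -0.49 to -0.51; 36-56% | -0.49 to -0.50; 43-71% |

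   In the first case the primary A1/A2 contrast averages about 0.00 and rejects 4.5 to 5.5%. Without the screening covariates, the planned model's miss in the second case is 0.10 to 0.22 SD and its rejection rate 6 to 11%.

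5. **Could Aim 1 rule out a V5 shift?** The 95% half-width for the V1-V5 change difference is 2.01 x sqrt(2(1 - rho)) x sqrt(2/24), or 0.64 SD at rho 0.4 and 0.58 at 0.5. Power for a 0.5 SD shift is 34 to 40% on the change score, and 46 to 50% with V5 adjusted for V1. The plan's 90 to 99% for the weekly interaction also reproduces, but on another scale. In the two-occasion case, f = d/2 with d = 0.4 is a 0.8 SD difference in change: (0.8)²/(1.2 x 2/24) = 6.4, the lambda in step 1.

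6. **Precision.** At r = 0.6, 0.7 and 0.8, the simulated SD is 0.27, 0.24 and 0.19 for the A1/V1-adjusted increment. It is 0.30, 0.28 and 0.23 for the planned model, and 0.36, 0.32 and 0.25 for the unadjusted (A2 - V5) - (A1 - V1).

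**The case against.** - **The plan predicts no V5 shift, and the model is secondary.** Both are true, and they limit the weight of the point. They do not remove it: the assumption is unstated, the protocol names a shift as a risk, and a non-significant weekly result at 24 per arm would not establish its absence.
- **The target is a choice.** The documents never define an A2 - V5 increment, and controlling for ad lib change can be read as a conditional effect. So the miss is an error only against the increment. But a comparison of arms at equal V5 pain is not protected by randomisation, and the increment is closer to the withdrawal-induced hyperalgesia that the Research Abstract names.
- **The replacement is more exposed in the direction the protocol names.** This stands. With V5 up and A2 unchanged, the increment contrast rejects more often than the planned model (41-72% against 11-34%). It correctly estimates a smaller step, but that step is not relief, so it needs a reading rule.
- **Both components are already modelled.** Also true. What is missing is their joint contrast with a standard error, and the rule.
- **The magnitudes are soft.** The correlations and shifts are assumed, and simpler fits give smaller misses. Equal same-phase correlations are assumed although V1 falls 7 days after A1 and V5 one day before A2.

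Two stronger readings are tempting. A reader might infer that the test of Hypothesis 1b is compromised; it is not, because the primary A1/A2 model does not use V5. A reader might also infer that the planned model will turn a general fall in pain into an abstinence benefit. No section predicts lower ad lib pain on VLNCs, so that row of the table is only an illustration.

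**Conclusion.** The point holds conditionally and is modest. If VLNCs shift V5, the planned secondary term for pain departs from the abstinence increment by about (1 - slope) x (V5 shift), less a withdrawal term. That is roughly 0.1 to 0.3 SD for an assumed 0.5 SD shift and same-phase correlations of 0.6 to 0.8. With no V5 shift the model is unbiased. The primary A1/A2 result is unaffected in every case. The algebra is firm; the sizes are illustrative. The gap to close is an unstated no-shift assumption, a missing direct contrast and a missing reading rule.

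**What to change.** In the secondary analyses of Specific Aim 1:

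1. Prespecify the group difference in A2 - V5, adjusted for A1, V1, screening pain, FTCD and sex, fitted separately for pain and for withdrawal.
2. Keep the V5-adjusted model as supportive, and state that it recovers the increment only if assignment does not shift V5.
3. Report the increment beside the primary A1/A2 contrast and the V1-V5 group difference, each with a 95% CI.
4. State that a smaller increment is described as attenuated withdrawal-induced hyperalgesia only if the primary A1/A2 contrast also favours VLNC with a CI excluding zero. Otherwise it is reported as a change in ad lib level.

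With V5 up and A2 unchanged, the rule holds the misleading label to at most about 5%, the primary contrast's rejection rate.

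**Cost.** Wording, plus one more secondary model per outcome, on data already scheduled in Table 1. Precision improves on the planned model if A1 and V1 enter as covariates. It worsens if an unadjusted change score is used, when power for a 0.5 SD increment is 26-47% against 43-71% adjusted. If people differ stably in hyperalgesia (assumed variance 0.4), the adjusted SD rises to 0.23-0.30. The rule is also demanding: at rho 0.4 the primary contrast has 70% power for a 0.8 SD difference in change but about 24% for 0.4 SD.
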